	
Kaplan-Meier to estimate probability of mortality in each arm
 
Construct a 95% confidence interval for the absolute difference between the two arms, <math>\Delta_{RD}</math>
 
Taking the type I error rate, alpha, to be 0.05, non-inferiority is concluded if the upper limit of a two-sided 90% = 100(1-2alpha)% confidence interval for <math>\Delta_{RD}</math> is less than the prespecified margin.
	
baseline; one clone assigned to each treatment strategy.
 
2. Person-time for each clones is censored when their observed treatment strategy is non-adherent. That is, clones assigned to undergo thyroid ultrasound within 3 months are censored at 3 months of follow-up if no ultrasound is performed. Similarly, clones assigned to not undergo an ultrasound within 3 months are censored at the time an ultrasound is performed.
 
3. A pooled logistic regression model is fit for the (conditional) probability of adherence, adjusting for a priori specified baseline factors that predict adherence.
 
4. A marginal structural pooled logistic regression model is fit to the mortality outcome data, as a function of time and treatment (with interaction), using inverse-probability of censoring weights from step 3.
 
5. Treatment-specific marginal probabilities of all-cause mortality are estimated from the fit in step 4, from which the causal risk difference, <math>\Delta_{RD}</math>, is estimated along with a two-sided 90% = 100(1-2alpha)% confidence interval (constructed via the bootstrap).
 
6. Taking the type I error rate, alpha, to be 0.05, non-inferiority is concluded if the upper limit of a two-sided 90% = 100(1-2alpha)% confidence interval for <math>\Delta_{RD}</math> is less than the prespecified margin.

Secondary Outcomes	
Cumulative over 7-years from PET:
 
Number of thyroid cancers
 
Number of thyroid ultrasounds
	
Cumulative incidence rate over 7-years from PET or to the end of the study period

	Number of thyroid biopsies Number of thyroid surgeries	
Exploratory Analysis	Types of thyroid cancer diagnoses	Same

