## 6 STUDY EXPOSURE

### 6.1 STUDY EXPOSURE DEFINITION

For this target trial emulation, exposure is whether a thyroid ultrasound is performed within 3 months of the index PET-CT.

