### **Explanation**

Exposure: 1 = thyroid ultrasound performed within 3-months following imaging examination; 0 = thyroid US not performed within 3-months following imaging examination

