### **Explanation**

Primary Outcome Binary: 1 = died within follow-up period; 0 = did not die within follow-up period

follow\_up\_in\_days

Primary Outcome Continuous: Number of days from imaging examination to death, 10-years, or end of study, whichever comes first

thyroid\_cancer\_dx\_post\_pet

Secondary Outcome Binary: 1 = ICD10 C73 diagnosis after PET exam; 0 = no ICD10 C73 diagnosis

post\_pet\_thyroid\_excision

Secondary Outcome Binary: 1 = CPT code 60100 for thyroid excision performed after PET exam

thyroid\_ultrasounds

Secondary Outcome Continuous: Number of thyroid ultrasound exams performed after PET exam

thyroid\_biopsies

Secondary Outcome Continuous: Number of thyroid biopsies performed after PET exam

thyroid\_cancer\_subtype

Exploratory Outcome: ICD10 C73 subcategory

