## Secondary Outcome Measure(s)

Hypotheses: Incidence rate ratios of (1) thyroid cancer diagnoses, (2) thyroid ultrasounds, (3) thyroid biopsies, and (4) thyroid surgeries are each higher in patients with an incidental thyroid nodule on PET-CT who had versus did not have thyroid ultrasound within 3 months.

Null hypotheses: Incidence rate ratios of (1) thyroid cancer diagnoses, (2) thyroid ultrasounds, (3) thyroid biopsies, and (4) thyroid surgeries are each not  $>1$  in patients with an incidental thyroid nodule on PET-CT who had versus did not have thyroid ultrasound within 3 months.

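### The thyroid-ultrasound outcome counts the scan that defines the ultrasound strategy, so its superiority hypothesis is largely built in

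*Combined protocol and SAP*

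**What the plan says.** **Exposure.** Section 6.1 states that "exposure is whether a thyroid ultrasound is performed within 3 months of the index PET-CT". The exposure variable in Section 7 is coded the same way: "Exposure: 1 = thyroid ultrasound performed within 3-months following imaging examination; 0 = thyroid US not performed within 3-months following imaging examination".

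**Outcome.** The ultrasound outcome in Section 7 is "Secondary Outcome Continuous: Number of thyroid ultrasound exams performed after PET exam". The secondary-outcomes row of the Section 1.2 table gives the window for the emulation: "Cumulative incidence rate over 7-years from PET or to the end of the study period".

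**Censoring.** Step 2 of the Section 1.2 table handles the two strategies as follows:
- Ultrasound strategy: "clones assigned to undergo thyroid ultrasound within 3 months are censored at 3 months of follow-up if no ultrasound is performed".
- No-ultrasound strategy: "clones assigned to not undergo an ultrasound within 3 months are censored at the time an ultrasound is performed".

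**Test and use.** Section 8.1 sets the secondary hypotheses: "Incidence rate ratios of (1) thyroid cancer diagnoses, (2) thyroid ultrasounds, (3) thyroid biopsies, and (4) thyroid surgeries are each higher in patients" who had the early ultrasound, against a null of a ratio not above 1. Section 8.4.1 treats these as superiority tests, judged by whether a two-sided interval for the difference excludes zero, and Section 8.4.4 sets the level at 95%. Section 3 says that differences in these outcomes will help to show whether the non-inferiority result matters clinically, and gives added morbidity as the reason. Section 4.1 allows the margin to be reconsidered in the light of secondary benefits.

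**The concern.** The exposure window and the outcome count both open at the PET-CT, and neither definition excludes the qualifying scan or the grace period. The scan that makes a patient adherent to the ultrasound strategy is therefore also an outcome event, in that arm only. A significant result would mostly restate the strategy definition and would say little about whether early ultrasound leads to more scanning afterwards.

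Weighting does not help. The inverse-probability weights change how much each clone contributes, not what is counted for it.

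At stake is the interpretation. One of four prespecified secondary hypotheses carries little information as written. Under Section 3, an excess that comes from the definition could be read as support for the non-inferiority conclusion.

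**Working it through.** The documents give no ultrasound rate, effect size or power for this outcome, so there is no planned figure to reproduce. The power statement in Section 8.2 concerns mortality only.

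**Step 1: what the definitions fix.** Under step 2 of the Section 1.2 table, every ultrasound clone followed past month 3 has a count of at least 1. Every no-ultrasound clone still uncensored at month 3 has a count of 0 for months 0 to 3. After month 3 a scan no longer censors a no-ultrasound clone, so both arms can accrue later scans.

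**Step 2: mean counts.** Let d be the share of the ultrasound arm that dies in the grace period before any scan. Let λ1 and λ0 be the later scan rates per person-year in the ultrasound and no-ultrasound arms, and T the mean follow-up in years.

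- Ultrasound arm: (1 − d) + λ1·T
- No-ultrasound arm: λ0·T

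Assumed ranges, not in the documents: λ from 0.02 to 0.30, T from 3 to 7, d from 0 to 10%.

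**Step 3: equal later scanning (λ1 = λ0 = λ).** The difference is 1 − d, which is 0.90 to 1.00 scans per patient. The rate ratio is [(1 − d) + λT] / (λT):

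| λ | T | d | Calculation | Ratio |
|---|---|---|---|---|
| 0.02 | 3 | 0 | 1.06 / 0.06 | 17.7 |
| 0.10 | 5 | 0 | 1.50 / 0.50 | 3.0 |
| 0.10 | 5 | 10% | 1.40 / 0.50 | 2.8 |
| 0.30 | 7 | 10% | 3.00 / 2.10 | 1.43 |

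**Step 4: how often the test would succeed with no later difference.** Later scans were simulated as Poisson with equal rates in the two arms and d = 10%. Each scenario had 2,000 runs, with an unweighted Wald test that succeeds when the lower two-sided 95% limit for the difference is above zero. Arm sizes (ultrasound / no ultrasound) are assumed.

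| λ, T | 25/100 | 50/200 | 200/800 |
|---|---|---|---|
| 0.05, 5 | 100% | 100% | 100% |
| 0.10, 5 | 100% | 100% | 100% |
| 0.30, 7 | 81% | 98% | 100% |

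With the strategy-defining scan left out of the count, the same scenarios gave 1.3% to 2.7%, against a nominal 2.5% in that direction.

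**Step 5: can the direction mislead?** Suppose early ultrasound halves later scanning: λ1 = 0.05, λ0 = 0.10, T = 5, d = 10%. The later ratio is 0.50. The planned outcome gives (0.90 + 0.25) / 0.50 = 2.30.

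**Step 6: can the hypothesis fail?** The arms are equal when λ0 = [(1 − d) + λ1·T] / T. With λ1 = 0.10 and T = 5 this is 1.40 / 5 = 0.28 (d = 10%) or 1.50 / 5 = 0.30 (d = 0), about three times the rate in the ultrasound arm. With no later scans in the ultrasound arm, λ0 = 0.20, T = 5 and d = 10%, the planned ratio is 0.90 / 1.00 = 0.90. Failure is therefore possible, but it needs about 0.9 to 1.0 more later scans per patient in the no-ultrasound arm.

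**The case against.** The best defence is that the estimand is legitimate. The target-trial column of Section 1.2 itself lists the number of thyroid ultrasounds over 7 years from the PET. Total use from time zero, including the assigned scan, is a valid contrast of utilisation between strategies, and it keeps outcome time aligned with the start of follow-up. Readers will also understand that an ultrasound strategy includes an ultrasound. This stands for a descriptive measure. It does not make the superiority test of that measure informative.

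A reader might infer that the hypothesis cannot fail. The documents do not support that. Only the month 0 to 3 part is fixed, and no-ultrasound clones may be scanned after the grace period without being censored. Enough delayed scanning in that arm would overturn the excess, as step 6 shows.

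A reader might also infer that the non-inferiority conclusion or its margin is compromised. That goes too far. Mortality is analysed separately, and Section 8.4.4 says that no secondary endpoint depends on the primary finding. The harms set out in Section 2.2 are overdiagnosis, overtreatment and surgical complications, and Section 4.1 names fewer biopsies and surgeries as the likely advantages. Neither makes ultrasound counts the main argument, so the route to the margin is limited. The interpretive route in Section 3 remains, because it covers all four outcomes.

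Finally, the size of the ratio rests wholly on assumed rates. That is right. The direction of the built-in contribution and its size of about one scan per patient do not depend on the assumed later rates.

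**Conclusion.** The concern holds as a should-fix point on one of four secondary outcomes. The strategy-defining scan is counted in the outcome, so a finding of more ultrasounds in the ultrasound arm is largely decided by definition.

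The built-in excess is 0.9 to 1.0 scans per patient if at most 10% of the ultrasound arm dies unscanned in the grace period. The ratio of about 1.4 to 18 and the simulated success rates are illustrations. They rest on assumed later rates, follow-up and arm sizes, and on an unweighted Poisson simulation rather than the planned weighted analysis. The primary mortality analysis is unaffected. Thyroid cancer diagnoses, biopsies and surgeries do not define the exposure, so they do not share this overlap.

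**What to change.** In the secondary-outcomes row of Section 1.2, the outcome list in Section 7 and the secondary hypotheses in Section 8.1:

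1. Report total thyroid ultrasounds from the PET as a descriptive measure of utilisation, outside the superiority rule in Section 8.4.1.
2. State, with reference to Section 3, that the strategy-defining scan is not counted as evidence of increased morbidity.
3. If a test is kept, apply it to ultrasounds after the 3-month grace period, in both arms, among clones still followed and with the censoring weights.

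The work is small: wording, plus one variable derived from scan dates that the censoring step already needs. Items 1 and 2 are enough to remove the uninformative test.

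Item 3 is optional and has downsides that the plan should state. It conditions on being alive and uncensored at month 3. It drops repeat scans in months 0 to 3. It also compares follow-up scans in one arm with delayed first work-up scans in the other, which is a different question from total use.

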### **Inclusion/Exclusion Variables**

thyroid\_nodule

### **Explanation**

Inclusion Criteria: 1 = thyroid nodule reported in imaging examination report; 0 = thyroid nodule not reported

age

Inclusion Criteria and Demographic: age in years at time of imaging examination

priorthyroidus

Exclusion Criteria: 1 = thyroid ultrasound performed within 3-years prior to imaging examination; 0 = thyroid US not performed within 3-years prior to imaging examination

priorthyroidcancer

Exclusion Criteria: ICD-10 C73 or ICD-9 193 before PET

NoSustainedCare

Exclusion Criteria: 1 = no provider note within system for 2-years following recommendation

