## 5 STUDY POPULATION

### 5.1 INCLUSION CRITERIA

In order to be included in this study, an individual must meet all of the following criteria:

1. Age  $\geq 18$
2. Thyroid nodule on PET-CT performed 1/1/2015 to 12/31/2021
3. At least one clinical note in the EHR from the 36-month window prior to the PET

Note, there are no restrictions on the indication for the index PET-CT.

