### 5.2 EXCLUSION CRITERIA

An individual who meets any of the following criteria will be excluded:

1. Prior PET reported thyroid nodule
2. Thyroid ultrasound listed in the medical record in the prior 3 years
3. Documented history of prior thyroid cancer diagnosis

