## 7 STUDY PROCEDURES

All of the following variables, except the last 12 disease status variables, will be extracted from the electronic health system research data warehouse using Snowflake, SQL scripts, and Python scripts. The extracted data will be coded as described in R. The last 12 disease status variables will be extracted and coded from the PET-CT reports by an instance of ChatGPT4 in Azure that is secure behind the healthcare system firewall. Data will be included for patients who had PET-CT examinations performed between 1/1/2015 and 12/31/2021, which allows a 3-year period for propagation of death records to our healthcare system's electronic health records. All HIPAA rules and local institutional and IRB requirements will be followed for data collection.

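### Prior thyroid cancer is excluded only through C73/193 codes before the PET, and any C73 code after it counts as an outcome, so an old cancer first coded after the PET is counted as new

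*Combined protocol and SAP*

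**What the plan says.** The criterion in Section 5.2 is "Documented history of prior thyroid cancer diagnosis", with no code, source or look-back limit. Section 1.2 states a similar exclusion. The only variable that applies it is priorthyroidcancer in Section 7: "Exclusion Criteria: ICD-10 C73 or ICD-9 193 before PET". Section 7 says that all variables outside the disease-status group "will be extracted from the electronic health system research data warehouse using Snowflake, SQL scripts, and Python scripts". The language-model extraction covers disease-status items from the PET report. None of these concerns past thyroid cancer.

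The secondary outcome thyroid_cancer_dx_post_pet is "Secondary Outcome Binary: 1 = ICD10 C73 diagnosis after PET exam; 0 = no ICD10 C73 diagnosis". The documents ask for no biopsy, surgery or pathology record in support, set no blanking window after the PET, and give no rule separating a new cancer from an old one.

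The pre-PET record required for entry (Section 5.1) is "At least one clinical note in the EHR from the 36-month window prior to the PET". Section 5.2 also lists two partial safeguards: "Thyroid ultrasound listed in the medical record in the prior 3 years" and "Prior PET reported thyroid nodule".

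**The concern.** The criterion concerns what is documented; the variable concerns what is coded, under two codes. A patient treated for thyroid cancer elsewhere or many years ago may carry that history only in note or report text, or under a personal-history code (to be confirmed against the code list). Such a patient meets the exclusion in Section 5.2 but passes the variable. If C73 is first entered after the PET, the old cancer is counted as an outcome.

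The weights cannot be relied on to correct this. They use the Section 7 covariates, and none records thyroid cancer history apart from the same kind of code: the general cancer indicator needs a code before imaging, and the head and neck indicator stops at C14.

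At stake is the thyroid-cancer contrast. Section 8.1 tests whether its rate ratio exceeds 1. Section 3 uses the secondary contrasts to judge whether a non-inferiority result is worth acting on. Section 4.1 allows the margin to be reconsidered in light of secondary benefits. Old cancers are not overdiagnosis of incidental nodules, so counting them blurs that reading. The exploratory subtype counts rest on the same code and share the error.

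**Working it through.** The plan gives no figure to reproduce here. The definitions come first, then a sensitivity calculation on assumed inputs.

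**1. Definitions side by side**

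| Patient | Meets the Section 5.2 exclusion? | Removed by priorthyroidcancer? | Counted if C73 appears after the PET? |
|---|---|---|---|
| C73 or 193 coded before the PET | Yes | Yes | Not in cohort |
| History documented, no C73/193 before the PET | Yes | No | Yes, as new |
| No history | No | No | Yes, correctly |

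The second row is the gap. The 3-year ultrasound exclusion and the prior-PET exclusion narrow it. Neither catches a patient with an older or outside cancer, no recent thyroid ultrasound and no nodule on an earlier PET report.

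**2. Leaked patients scanned more often than the rest**

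Assumptions, none from the documents: 20% of the cohort scanned; 7-year incidence of new thyroid cancer 3% in both arms; a share f of the cohort leaked; a share s of leaked patients scanned; all later coded C73. The risk ratio stands in for the rate ratio, and the split is crude rather than weighted.

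- Added risk, ultrasound arm: s·f/0.2. Added risk, no-ultrasound arm: (1−s)·f/0.8.
- With s = 0.5: ratio = (0.03 + 2.5f)/(0.03 + 0.625f).
- f = 0.25%: 0.03625/0.03156 = 1.15.
- f = 0.5%: 0.0425/0.03313 = 1.28.
- f = 1%: 0.055/0.03625 = 1.52.
- With s = 0.3 and f = 0.5%: 0.0375/0.03438 = 1.09.
- With s = 0.2, the cohort rate, both arms gain f and the ratio stays 1.00.

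Removing leaked patients from the 3% baseline changes the three s = 0.5 results only to 1.14, 1.28 and 1.50.

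**3. The same model with a true ratio of 2 (assumed 6% vs 3%)**

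Ratio = (0.06 + 5s·f)/(0.03 + 1.25(1−s)·f). It exceeds 2 only if 5s > 2.5(1−s), that is s > 1/3. At s = 0.3 and f = 0.5% it is 0.0675/0.03438 = 1.96, a slight dilution.

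**4. Equal leak, unequal re-coding**

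Let u be the leaked share, the same in both arms, and c the chance of a first C73 code after the PET. Observed risk = (1−u)·incidence + u·c. Section 2.2 gives 1.1% of people as ever diagnosed, the only thyroid cancer frequency in the documents. It serves here as an anchor for incidence and as the upper end of u, which runs from 0.1% to 1.1%. The values of c and the 3% are assumed.

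| True incidence, ultrasound / none | True ratio | c = 80% / 80% | c = 80% / 40% | c = 80% / 20% |
|---|---|---|---|---|
| 1.1% / 1.1% | 1.00 | 1.00 | 1.04 to 1.29 | 1.05 to 1.50 |
| 3% / 1.1% | 2.73 | 2.61 to 1.95 | 2.70 to 2.52 | 2.75 to 2.94 |

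In the first row, old cancers make up 7% to 45% of the cancers counted in the ultrasound arm, even where the ratio does not move. On the risk-difference scale, which Section 8.4.4 also allows, equal re-coding at u = 1.1% barely matters in the second row: 1.90 points become 1.88. With 80%/20% they become 2.54.

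**5. Mortality**

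At f = 1% and s = 0.5, leaked patients are 2.5% of the ultrasound arm and 0.625% of the other. An assumed 20-point mortality gap between leaked and other patients would move the risk difference by (2.5% − 0.625%) × 20 = 0.375 points, against a 5-point margin.

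**The case against.** Applying a history exclusion through diagnosis codes is how Section 7 handles most comorbidities. The variable has no look-back limit and includes the ICD-9 code, so older coded cancers are caught. An outside cancer entered locally as C73 or 193 before the PET is caught as well. One note is a minimum, not the typical record. Leak fractions of 0.25% to 1% are 23% to 91% of the 1.1% in Section 2.2, and these patients must also pass the ultrasound and prior-PET exclusions. Assuming that all of them later receive C73 sits awkwardly with the reason they were missed.

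All of this bears on size, and it stands: the leak may be small. It does not remove the mechanism, because no text source or incident-case rule backs up the codes.

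A reader might go further and infer that old cancers will be counted as cancers found by ultrasound and so inflate the ratio. The documents do not support that. The outcome has no link to ultrasound, and old cancers count in both arms. Inflation needs a known history to make ultrasound or re-coding more likely. That is plausible, but nothing in the documents shows it, and steps 3 and 4 show dilution under other assumptions.

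A reader might also infer that the primary analysis is compromised. Step 5 puts that effect below 0.4 points even under unfavourable assumptions.

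**Conclusion.** The concern holds as a misclassification of the secondary thyroid-cancer outcome and the exploratory subtype counts. Followed as written, the plan keeps some patients whom Section 5.2 excludes and can count their old cancers as new. The mechanism rests on the definitions alone.

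Direction and size do not. The leaked share, the share of those patients scanned and the chance of re-coding are all absent from the documents. Across the assumed ranges, a true ratio of 1.0 is observed anywhere from 1.00 to 1.52, and a true ratio above 1 may rise or fall. This should be settled before the outcome is extracted. It is not a threat to the mortality conclusion.

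**What to change.** Make two changes in Section 7, and align the wording of Section 5.2 with them.

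1. **Exclusion.** Extend priorthyroidcancer to include a history of thyroid cancer, or of thyroidectomy for cancer, stated in the index PET report. This is one added field in the language-model read already planned. Add any personal-history-of-thyroid-cancer code once confirmed against the code list. Do not exclude on a thyroidectomy code alone: that would remove patients operated on for benign disease, whom Sections 5.1 and 5.2 leave eligible.
2. **Outcome.** Define an incident case as a first C73 code after the PET with a supporting post-PET thyroid biopsy, surgery or pathology record, at least as a sensitivity analysis beside the code-only count. Biopsy and excision variables are already listed in Section 7; a pathology record would be an addition.

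Both are needed. A recurrence biopsied after the PET would meet the incident-case rule and only the exclusion removes it; a history absent from the PET report escapes the exclusion, and the incident-case rule may still catch it.

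The cost is one extra language-model field, a few codes, a slightly smaller cohort and slightly fewer counted cancers. Some lost cases will be genuine new cancers whose supporting record lies outside the health system, which is a reason to report both counts.

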### 1.2 TARGET VS. EMULATED TRIAL TABLE

	Target Clinical Trial	Observational Emulation
Design	Non-inferiority randomized controlled trial	Retrospective non-inferiority cohort study
Aim	Assess whether all-cause mortality in patients with an incidental thyroid nodule on PET-CT who did	Same

	not have thyroid ultrasound within 3 months is no worse than 5% higher than those who did have ultrasound	
Inclusion	Thyroid nodule on PET-CT Age 18 or older Clinic note within 36-months before the PET-CT	Same, with PET-CT scans between 1/1/2015 to 12/31/2021
Exclusion	Prior PET reported thyroid nodule Thyroid ultrasound in prior 3 years Prior thyroid cancer diagnosis	Same
Treatment Strategies	(1) Thyroid ultrasound ordered to be performed within 3 months (2) No thyroid ultrasound ordered	(1) Thyroid ultrasound performed within 3 months (2) No thyroid ultrasound performed within 3 months
Treatment Assignment	Randomized to treatment strategy	Non-randomized to treatment strategy. Randomization emulated via cloning patients in both arms.
Treatment Implementation	3-month grace period	3-month grace period
Outcome	All-cause mortality	Same
Type of Outcome	Failure time	Same
Follow-up Start	PET-CT date, equivalent to treatment assignment	PET-CT date, not equivalent to treatment assignment
Follow-up End	Earliest of death, 7-years from follow-up start, or study end	Same
Censoring	Administrative censoring	Administrative censoring Artificial censoring of clones
Causal Contrast	Intention to treat and per protocol	Per protocol effect only
Non-Inferiority Margin	5%	Same
Statistical Analysis	Non-inferiority intention to treat analysis that consists of comparing probability of mortality between treatment groups at 7 years.	Non-inferiority analysis using clone-censor-weight strategy: 1. Each subject is cloned at study

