### 6.3 LOST TO FOLLOW-UP

Complete mortality data is available in the electronic health record via regular updates from electronic death registry systems and from 5 state death registries, regardless of patients' continued care within the study healthcare system; so there is no loss to follow-up for the primary outcome. The 3-month grace period between the PET examination and the ultrasound will be addressed with clone-censor weighting. For the secondary outcomes, we will consider patients who did not have any provider note for 2-years following the PET-CT to be lost to follow-up.

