## 8.3 POPULATIONS FOR ANALYSES

Single dataset for per-protocol analysis including all patients who met the inclusion/exclusion criteria.

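### Section 7 labels NoSustainedCare, a variable built on later notes, an exclusion; Sections 1.2, 5.2 and 6.3 do not, so the primary analysis set is ambiguous

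*Combined protocol and SAP*

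**What the plan says.** Section 7, under Inclusion/Exclusion Variables, defines NoSustainedCare as "Exclusion Criteria: 1 = no provider note within system for 2-years following recommendation". No section says what the recommendation is or when it is dated.

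The formal list in Section 5.2 opens with "An individual who meets any of the following criteria will be excluded" and has three entries. All look backward from the PET-CT, for example "Thyroid ultrasound listed in the medical record in the prior 3 years". The exclusion row of the Section 1.2 table gives the same three and marks the emulation as the same as the target trial. The only care-contact rule in Section 5 also looks backward: "At least one clinical note in the EHR from the 36-month window prior to the PET".

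Section 6.3 uses the two-year note rule differently. For the secondary outcomes, "we will consider patients who did not have any provider note for 2-years following the PET-CT to be lost to follow-up". For mortality, it says that deaths are captured whether or not the patient stays in the system, "so there is no loss to follow-up for the primary outcome".

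Section 8.3 then defines the analysis population: "Single dataset for per-protocol analysis including all patients who met the inclusion/exclusion criteria".

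**The concern.** Follow-up starts at the PET-CT date (Section 1.2). A rule that needs up to two years of later notes cannot be applied at that date, so using it for eligibility breaks the alignment of eligibility with time zero on which a target trial emulation rests. The rule has no exemption for death: a patient who dies without a further note is dropped, and the primary event goes too.

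Section 7 is what the programmer works from when extracting and coding the data. A programmer who follows its label drops these patients from the single dataset; one who follows Section 5.2 keeps them. A pre-specified non-inferiority analysis should not allow two primary populations.

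The secondary outcomes have a separate weakness that remains whichever way the conflict is settled. Under Section 6.3 a single note soon after the PET-CT, say at month 1, is enough not to be counted as lost. If that patient then leaves, later ultrasounds, biopsies, operations or cancers elsewhere are missed while follow-up still accrues for up to 7 years. Section 8.4.4 reuses only the ultrasound-adherence weights, and no censoring date or weight for loss of contact is given.

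**Working it through.** **Plan's own figure.** There is none to reproduce. The documents give no count of patients without notes, overall or by ultrasound status. The stated power of at least 75% comes with no analysis sample size and does not bear on this point.

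**Passages side by side**

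| Section | Is the two-year note rule an exclusion? | Counted from | Applies to |
|---|---|---|---|
| 1.2, 5.2 | Not listed | – | – |
| 6.3 | No, loss to follow-up | PET-CT | Secondary outcomes only |
| 7 | Yes, by its label | Recommendation (undefined) | Not limited |
| 8.3 | Not named; one dataset from the criteria | – | All analyses |

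**How the bias would arise.** Each patient is cloned into both arms. Ultrasound-arm clones without an ultrasound are censored only at 3 months (Section 1.2, step 2). A no-ultrasound patient who dies before 3 months is therefore a death in both arms, and removing that patient lowers both. After 3 months, the removal affects only the no-ultrasound arm. The rule thus acts differently by arm mainly through patients still alive at 3 months, and only to the extent that having an ultrasound makes a note more likely. The weights in step 3 use baseline predictors of adherence and do not model the presence of later notes.

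**Crude one-arm shift (all inputs assumed).** Let k be mortality among no-ultrasound patients kept, f the fraction removed and m the mortality of those removed. Then shift = k − [f·m + (1 − f)·k] = f·(k − m). With k = 30%:

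- f = 5%, m = 50%: 0.05 × (−20) = −1.0 point
- f = 10%, m = 60%: 0.10 × (−30) = −3.0 points
- f = 5%, m = 20%: 0.05 × 10 = +0.5 point
- f = 10%, m = 15%: 0.10 × 15 = +1.5 points

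Mortality in that group is understated by 1.0 to 3.0 points if those removed are sicker, and overstated by 0.5 to 1.5 points if they are healthier.

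As a second anchor, let p be mortality in the whole no-ultrasound group, so that shift = f·(p − m)/(1 − f). Take p = 39.5% (Section 8.2, a 10-year figure from CT and MRI patients, used only for scale). A 5-point shift then needs f = 0.05/(|p − m| + 0.05): 9% for m = 90%, 14% for m = 70% or 10%, and 20% for m = 20%.

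**Clone-censor simulation (all inputs assumed).** There was no true effect. Each scenario had 2,000,000 patients, one measured binary covariate that doubles the hazard, about 20% with ultrasound within 3 months and 7-year mortality of about 38%. Estimates were made within covariate strata and averaged over the analysed cohort, in place of the plan's weighting. Risk difference is no ultrasound minus ultrasound, in points. Leavers never have a note unless an ultrasound produces one, and they are drawn regardless of prognosis.

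| Ultrasound produces a note? | Leavers | Notes per year | Cohort removed | Without exclusion | With exclusion |
|---|---|---|---|---|---|
| Always | 0% | 12 | 0.5% | +0.16 | +0.12 |
| Always | 0% | 4 | 1.5% | +0.01 | −0.42 |
| Always | 0% | 2 | 4.1% | −0.08 | −1.24 |
| Always | 0% | 1 | 14.3% | +0.08 | −1.95 |
| Always | 10% | 12 | 8.6% | −0.18 | −0.22 |
| Always | 15% | 2 | 15.6% | −0.09 | −1.30 |
| Not by itself | 10% | 4 | 11.6% | +0.07 | +0.06 |
| Not by itself | 0% | 2 | 4.9% | −0.10 | −0.08 |

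Simulation noise is about ±0.2 point. In the fourth row, mortality fell from 37.9% to 34.8% without ultrasound (3.1 points) and from 37.8% to 36.8% with it (1.0 point). The ultrasound arm falls too, so a one-arm shift can overstate the effect on the tested difference. In the last two rows the removal rates are similar by ultrasound status (11.7% without against 10.9% with, and 5.1% against 3.9%), and no bias is visible.

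The simulation has no scenario in which leavers are healthier than those who stay, so it cannot show bias away from non-inferiority. Its range is an illustration, not a bound.

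**The case against.** The strongest reply is that the label is leftover text. Sections 5.2 and 1.2 omit the rule, 6.3 confines it to secondary outcomes, and the criteria meant in 8.3 are most naturally those of Section 5. The Section 7 list is also not a complete eligibility list: it has no variable for a nodule reported on a prior PET, nor for the 36-month note requirement. This stands in part. A reader might infer that the exclusion definitely reaches the mortality analysis; the documents support only that they contradict each other on it. The label is still in the coding specification with no limit to secondary outcomes, so the conflict remains.

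A reader might also infer that nearly all removals come from patients without ultrasound, because an in-system ultrasound would generate a note. That is plausible, but the documents neither define a provider note nor say whether an ultrasound visit or report counts. In the simulation the removals fall wholly on no-ultrasound patients only where every ultrasound is assumed to produce a note.

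Finally, censoring secondary follow-up at the end of contact also relies on a gap seen in retrospect, and is one choice among several. That is fair, but a dated rule with weights is preferable to crediting full follow-up on one early note.

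**Conclusion.** The concern holds as an internal contradiction about the primary analysis set, with possible selection bias on one of its two readings. It should be settled before analysis. That the variable uses post-baseline information, that 1.2 and 5.2 omit it, and that 6.3 gives the same rule another role are all plain from the text. By 6.3's own account of death ascertainment, the primary analysis does not need the exclusion.

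It would go too far to say that the plan is biased toward non-inferiority. Removing patients who die without a further note pushes that way; removing well patients who left pushes the other way. On assumed inputs the simulated effect on the tested difference ran from about 0 to −2.0 points against the 5-point margin, and the crude one-arm shift from 3.0 points understated to 1.5 points overstated. These figures rest on assumed removal fractions, mortality among those removed, ultrasound share and note frequency, none of which the documents give. The weakness in secondary follow-up does not depend on how the contradiction is resolved.

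**What to change.** - Delete NoSustainedCare from the exclusion variables in Section 7. State in 8.3 that the primary analysis keeps every patient who meets 5.1 and 5.2, whatever notes follow.
- For secondary outcomes, replace the all-or-nothing rule with censoring at the end of in-system contact (for example, at the start of a two-year gap in notes). Add a censoring-weight model using the Section 7 baseline covariates, and fix the rule in writing before analysis.
- Count from the PET-CT date throughout, and define what counts as a provider note, including whether an ultrasound visit or report does.
- Report the number of patients with no later note by ultrasound status and vital status, so that readers can judge the size of the issue.

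For the primary analysis this is a wording change that brings Section 7 into line with 1.2, 5.2 and 6.3. For the secondary outcomes it adds one weight model, needs encounter dates from the same data warehouse, and somewhat shortens follow-up.
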